Study	Frequency (Pulse Rate, Hz)	Width (Pulse Width, Microseconds)	Amplitude	Comments	Effect
Bai	2-100			Transcutaneous Posterior Tibial, Dysmenorrhea, frequency not controlled or compared	Efficacious for Dysmenorrhea
Lauretti	85		variable	Transcutaneous Suprapubic, Dysmenorrhea	Efficacious for dysmenorrhea pain and QOL
Lee	100	100		TENS lower abdomen and thermotherapy for Dysmenorrhea	Efficacious for dysmenorrhea pain and QOL
Buffenoir	100-200	1.4-8.7		Implanted spinal cord stimulation for pudendal neuralgia	Efficacious for decreasing pain
Comiter	16	210		Sacral nerve stimulation, Interstitial cystitis	Effective to reduce pain
Ghazwani	14	200		Sacral nerve stimulation, Bladder pain syndrome	Effective to reduce pain

Kaplan	100	95	50	TENS, Dysmenorrhea,	Effective for pain
Kim	20		10	PTENS(Percutaneous electrical nerve stimulation), chronic pelvic pain	May be helpful for pain but was not statistically significant
Maher	15	210		Percutaneous S3 Sacral Nerve Stimulation, Interstitial Cystitis	Improved pelvic pain, nocturia
Schneider	80	150		Transcutaneous penile electrodes, pain scale and QOL	Reduced pain and increased QOL
Tugay	120	100		Transcutaneous Lower Back, Dysmenorrhea	Not statistically significant for dysmenorrhea
Vallinga	80	50-180		TENS (Location not specified), Vestibulodinia	Reduced Vulvar pain
Van Balken	20	200	0-10	Percutaneous, Posterior tibial nerve, Chronic pelvic pain	Reduced pain and improved QOL

The goal of the current study is to determine which pulse rate (Hz) is the most effective to use in posterior tibial transcutaneous electric nerve stimulation for treating pelvic pain given a set location (posterior tibial nerve) and Pulse Width (200 microseconds) on continuous stimulation.

Specific Aim: To determine if a low (Group 1, 20 Hz), medium (Group 2, 50Hz), or high (Group 3, 100 Hz) pulse rate (frequency) used in posterior tibial TENS is better in improving pelvic pain (as measured by decreased Visual Analog Scale (VAS) scores and improved pain, urinary and QOL scales on the validated Genitourinary Pain Index (GUPI).

Hypothesis: A high frequency (100 Hz) used in TENS will show the most improvement in pelvic pain compared to low and medium frequencies.

B. STUDY DESIGN

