The participants will be randomized into three groups of 25 participants each. The randomization will occur in blocks so that if we need to terminate the study early there will be an equal number of participants in each group. The size of the blocks will also be kept secret for allocation concealment purposes. The randomization will be stratified by gender so that there is an equal number of participants from each gender in each group, reducing potential for gender as a confounding variable. Group 1 will be the low frequency set at 20 Hz. Group 2 will be the medium frequency set at 50 Hz. Group 3 will be the high frequency set 100 Hz. There is no sham group in this study as it has previously been found that posterior tibial TENS is effective and lasting. As such, all participants will be treated as a matter of routine medical care for pelvic pain. We will use a fixed pulse width of 200 microseconds (uS), with continuous rather than biphasic stimulation based on input from 5 colleagues with expertise in neurophysiology and TENS and on the above literature review. We will aim to recruit 25 participants per group for a total of 75 participants.

Study Procedures

Participants with chronic/persistent pain that has been continuous or recurrent for at least three months (in accordance with EAU Guideline definition) who have failed first line treatment will be advised of the study. All participants will be asked if they have an adhesive allergy and medical record reviewed for this allergy as this will exclude them from the study. A detailed explanation of the purpose of the study, along with the risks and benefits of TENS will be given to the participant by a provider prior to obtaining informed consent for enrollment into the study. After informed consent has been obtained, if the participant is of childbearing potential, a urine pregnancy test will be conducted. The participant will be excluded from participation if pregnant and referred for appropriate care.

Study Schedule Overview:

	Standard Visit Billed in Part to Insurance	Just a Study Visit	Virtual Phone or Video is an Option	In Person Only	Questionnaires: 1-10 pain scores and GUPI	Usage Chart Completed (During phase when TENS being Used)	Treatment Map Completed / Updated with Dates	Adjusting TENS Settings Permitted	New Treatments outside of pre-existing treatment and TENS Permitted
Week 1 – Phone Call in Response to Mailer		√	√		√		√		
Week 1 – Occurring as Part of Regular Office Visit	√		√		√		√		

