All subjects will be analyzed according to the intention-to-treat [ITT] principle. A participant will be considered evaluable and will be included in the intention-to-treat analysis if the participant has documented at least 8 sessions of their designated TENS treatment (about 4 times a week of TENS therapy). Analyses that take into account the actual treatment received (e.g., non-compliance, etc.) will be carried out as a secondary analysis (per protocol [PP] analysis).

Primary Statistical Objective:

The primary objective of the study is to compare the three TENS treatment groups after two weeks of active treatment, with respect to:

The change in VAS and GUPI pain questionnaires from baseline to after two weeks of

therapy.

The proportion of responders after two weeks of therapy.

Secondary Statistical Objectives:

Secondary objectives include comparison of the three treatment groups with respect to the rating of VAS and GUPI scores, separately, over time (by weekly diary entries). Analysis will be carried out to determine if there are time-dependent changes in questionnaire scores across the three TENS treatment groups. Urinary symptoms and individual pain site questions will be noted.

Pairwise comparisons of TENS groups will also be carried out to compare each arm with one another using Tukey's multiple comparison tests.

We will again collect data at 1,2-, and 3-months post-trial, asking how much the TENS has been used, to assess durability.

Outcome Variables and Schedule of Assessments:

The primary outcome variable of interest is participant's percentage change in VAS and GUPI from before treatment to the end of 2 weeks of active TENS. Also evaluated will be the response to treatment each week during the 14-day TENS therapy period and the 2 weeks of observation. A participant is said to have a favorable response to the treatment if he/she has a decrease of at least 2 points on the VAS or 1 point on the GUPI question #9 from baseline to after two weeks of TENS therapy. Change in outside interventions will not be permitted during the study but stable therapies will be maintained (e.g., medications).

Demographics and participant characteristics will be collected at baseline (age, gender, medical history, surgical history, current medications, site of pain, duration of chronic pelvic pain). The following outcomes will be measured at baseline, at each week, and at 3 months after the TENS therapy month:

- VAS Weekly Scores
- GUPI Weekly Scores

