Statistical Methods

For the primary objectives:

- Analysis of variance with a fixed effect of treatment with Tukey's multiple comparison test will be used to test for differences in the reduction in genitourinary symptoms among the three treatment arms. Reduction will be parameterized as a relative change from baseline to after the two weeks of treatment. VAS pain response before and after treatment will be compared among the three groups using repeated measures ANOVA with Tukey's multiple comparison tests.
- The Chi-square test or Fisher's exact test, as appropriate, will be used to compare the rates of response among the three treatment arms at the end of the 14-day treatment period.

For the secondary objectives, a repeated measures analysis of variance will be used to analyze the outcomes of interest on a week-to-week basis (improvement in GUPI scores). A treatment-by-time interaction will be examined to determine if the patterns of change in GUPI and VAS scores over time differ across groups. Adjusted pairwise comparisons (Tukey or Bonferroni method) will be used to compare treatment groups to one another.

Data transformations may be applied, if necessary, in order to meet the required standard model assumptions.

Sample Size Considerations

Power: The number of participants needed was based on a power calculation (ANOVA with 2-tailed alpha of 0.05) assuming that the minimally important difference to detect among the three groups in the change in VAS score would be at least one within-group standard deviation of the change in score at 14 days. With 21 participants per group the power is estimated at 81%. We propose to randomize 25 per group assuming the dropout rate may be as high as 20%.

Based on investigator expertise and some published studies, we assume that the proportions of responders based on our criteria of a “favorable response” for each of the three TENS groups will be around 40 % (1,2,4,7,10). In our study we are aiming for at least a 40% response rate in our complex and refractory population.

Conduct of the study

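### Randomising 25 per group at the stated 20% dropout leaves 20 per group, not the 21 on which the 81% power rests; on the most likely basis power is then about 79%.

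*Combined protocol and SAP*

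**What the plan says.** The power statement is in section D (Data Analysis), under Sample Size Considerations. It describes an ANOVA with a 2-tailed alpha of 0.05 on the change in VAS. The smallest difference of interest among the three groups "would be at least one within-group standard deviation of the change in score at 14 days". It continues: "With 21 participants per group the power is estimated at 81"%, and then: "We propose to randomize 25 per group assuming the dropout rate may be as high as 20"%.

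Section B (Study Design) repeats the recruitment target: "We will aim to recruit 25 participants per group for a total of 75 participants". Neither section gives the power at any other number per group, the location of the third mean, or the rule used to get from 21 to 25.

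Three other statements bear on what the 81% refers to:

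- The Primary Statistical Objective is an overall comparison: "The primary objective of the study is to compare the three TENS treatment groups after two weeks of active treatment".
- The Secondary Statistical Objectives list the pairwise tests: "Pairwise comparisons of TENS groups will also be carried out to compare each arm with one another using" Tukey's method. Statistical Methods, however, places Tukey tests under the primary objectives as well: "VAS pain response before and after treatment will be compared among the three groups using repeated measures ANOVA with" Tukey's tests.
- The hypothesis at the end of section A is directional: "A high frequency (100 Hz) used in TENS will show the most improvement in pelvic pain compared to low and medium frequencies".

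**The concern.** The allowance for dropout exists so that the number behind the power calculation is still there at the end. Here the plan names a worst-case loss and a number to randomise, and together they give one participant fewer per group than the power calculation uses. With 25 randomised, 21 remaining and 20% dropout cannot both hold.

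At stake is the accuracy of the stated sample-size basis. A reader takes the paragraph to promise 81% power even at the dropout limit. On the most likely basis for that figure, the limit takes power from just above 80% to just below it.

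**Working it through.** **Inputs.** From Sample Size Considerations: ANOVA, alpha 0.05, difference of 1 within-group SD, 21 per group for 81% power, 25 randomised per group, dropout up to 20%. From section B: 75 in total. Allocation is equal (Randomization, section D). The position of the middle mean is not given, so it is varied below.

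**Step 1: dropout arithmetic (no assumption needed).**

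- Remaining at 20% loss: 25 × (1 − 0.20) = 20 per group.
- Largest loss that keeps 21: 1 − 21/25 = 16%.
- Number needed to keep 21 at 20% loss: 21 / 0.80 = 26.25, so 27 per group and 3 × 27 = 81 in total.
- A possible origin of the slip is 21 × 1.2 = 25.2, rounded down to 25. The plan does not show this step.

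**Step 2: reproduce the 81%.** For a one-way ANOVA with three groups of size n, power is the probability that a noncentral F variable with 2 and 3(n − 1) degrees of freedom exceeds the 5% critical value. The noncentrality is λ = n × Σ(group mean − grand mean)² / SD².

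With means 0, 0.5 and 1 SD, the sum of squares is 0.25 + 0 + 0.25 = 0.5. At n = 21, λ = 10.5 and the degrees of freedom are 2 and 60. Power is 81.5%, which matches the stated 81%.

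Other bases at n = 21 fit less well: two groups equal 91.5%, an unadjusted two-sample t-test 88.5%, a single Tukey pair 79.6%, a Bonferroni pair 77.9%. The Tukey pair is the nearest rival, but the F-test is closer and is the test the paragraph names.

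**Step 3: power at the number that remains.** At n = 20 with the middle group midway, λ = 10.0, the degrees of freedom are 2 and 57, and power is 79.3%.

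| Middle group (largest difference exactly 1 SD) | 20 per group | 21 per group | 25 per group |
|---|---|---|---|
| Midway (least favourable for the F-test) | 79.3% | 81.5% | 88.3% |
| A quarter of the way along | 82.6% | 84.6% | 90.8% |
| Equal to one of the other groups | 90.0% | 91.5% | 95.7% |

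If the 81% came instead from a single Tukey pair 1 SD apart, power would go from 79.6% at 21 to 77.3% at 20.

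**Step 4: sensitivity to the effect size.** With 20 per group and the middle group midway, a largest difference of 1.03 SD (1.026) restores 81.5%.

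**Step 5: what the figure does not cover.** The section A hypothesis needs 100 Hz to beat both other groups. By simulation, with Tukey's test at 20 per group (critical t 2.406 on 57 degrees of freedom), a largest difference of 1 SD and both comparisons required to be significant, power is about 20% with even spacing. It is about 44% if 50 Hz lies a quarter of the way from 20 Hz, and about 65% if 20 and 50 Hz are equal. The plan sets none of these patterns, so this is context for reading the 81% and not part of the error.

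**The case against.** The strongest reply is that this is minor. The 20% is an upper bound and not an expected rate; up to 16% dropout the stated 21 and 81% are kept. The loss is about 2 points, and the plan allows for a difference larger than 1 SD, where 1.03 SD already makes up the gap. All of that is right and limits the size of the point. It does not remove it: the upper bound is the plan's own reason for randomising 25, and 25 does not protect 21 at that bound.

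A second reply is that the 79% is inferred. That also stands. The plan does not place the middle group, midway is the least favourable position for the F-test, and a quarter of the way along gives 82.6% even at 20 per group. But midway is the pattern that best reproduces the plan's 81%, so the before-and-after comparison belongs there. The shortfall of 20 against 21 does not depend on it.

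Third, dropout need not mean loss from the analysis. The Intention-to-Treat paragraph counts anyone with at least 8 documented sessions, so a late dropout might still be included, while a participant who stays but uses the device too little would be excluded. The plan does not say whether the 20% covers such exclusions, so the net direction is unknown.

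Finally, the paragraph claims no power for showing 100 Hz best. That is fair, and the pairwise figures are offered only as a clarification.

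**Conclusion.** The concern holds. The stated allowance leaves 20 per group at 20% dropout, one short of the 21 behind the power figure. This follows from the plan's own three numbers, taking dropout as loss from the analysis.

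The effect on power is small. It is about 2 points (81.5% to 79.3%) if the test is the overall F-test, the largest difference is exactly 1 SD and the middle group lies midway. At 20 per group the overall test has between 79.3% and 90.0% power for a 1 SD range, depending on the middle group. The paragraph is wrong as written, but the design is not undermined.

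**What to change.** Amend the Sample Size Considerations paragraph.

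1. Confirm the test and the middle-group position behind the 81%, and state them.
2. Then use one of two wordings. Either say that 25 randomised per group keeps 21, and hence 81% power, for dropout up to 16%; this needs no inferred assumption. Or say that 25 randomised leaves 20 per group at 20% dropout, with about 79% power for the overall ANOVA test if the largest difference is 1 SD and the middle group is midway, which is the least favourable position.
3. State that the figure is for the overall three-group test and not for showing 100 Hz better than both other frequencies.

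Optionally, report Tukey power for the section A hypothesis as a range with its assumptions, and settle whether the pairwise comparisons are primary or secondary.

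The cost is the wording of one paragraph and, with the second wording, a stated power about 2 points lower. No participants are added and neither design nor analysis changes. Keeping 21 per group at 20% loss would instead take 81 − 75 = 6 more participants; that is the sponsor's choice and is not requested.

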The principal investigator, [name] MD, is responsible for overall oversight of the data, monitoring the data, assuring protocol compliance, and conducting the safety reviews. The principal investigator will also be responsible for compiling the data sheets, day to day oversight of research and ensuring the integrity and privacy of the data. During the review process the principal investigator, along with the other investigators, will evaluate whether the study should continue unchanged, require modification/amendment, or close to enrollment. The principal investigators or the Institutional Review Board (IRB) have the authority to stop or suspend the study or require modifications.

The master key will house PHI relating to name, address, phone number, MR number and date of birth. The secure Qualtrics survey obtained weekly from participants will be securely downloaded as an excel spreadsheet into a protected AMC Onedrive file accessible only to study personnel. This spreadsheet will be uploaded directly to the secure one drive account to ensure participant confidentiality and security of PHI. Paper surveys will be entered into this database within Onedrive. The master key and database will be stores in separate protected Onedrive files.

Any worsening symptoms or adverse reactions will be reported to the examiners, by way of pain questionnaire, phone calls to participants, the 14-day clinic visits, or reported by participants aside from these instances. For participants with any severe or persistently worsening symptoms or adverse reactions, TENS therapy will be immediately discontinued, they will be removed from the study and considered to have failed treatment and receive medical treatment as necessary. Skin irritation is the most common adverse reaction to TENS units; however, this is mostly associated with allergy to the self-adhesive electrodes (12). While pain may be a

complication with TENS, studies have shown TENS is actually beneficial in treatment of pain over different areas of the body (12).

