Participants with contraindications to TENS (eg, other electrical devices, pregnancy, bleeding or clotting disorders, unhealthy tissue, seizure disorders, malignancy, impaired cognition, adhesive allergy) will be excluded from the study. Participants will be taught safe practice with the use of a TENS unit, such as performing a sensory discrimination test in the office, checking and cleaning skin before starting a TENS session, monitoring skin for signs of irritation, changing adhesive on electrode pads after each use, securing electrodes with even pressure distribution and full contact, and watching for signs of TENS unit malfunction requiring maintenance [11].

Participants will be instructed to adjust the intensity to the level they can tolerate, so if the TENS intensity is too high then the participants will not be able to tolerate. Pain is the main issue with increased intensity (when it is not used to actually treat pain), therefore intensity will be minimized as per protocol to prevent this (“to the participant’s perception and tolerance”). Increased intensity would be assumed to lead to skin break down, however, reports of this are exceedingly rare (13). Participant education will be comprehensive here.

While reports of dermatitis have been reported in the literature, in most of these cases the dermatitis is caused by an allergy to the adhesive on the TENS electrode pads and not the actual electrical stimulation. Skin irritation can occur, but this is mostly seen in cases where TENS therapy has been used for multiple hours in a row. There has been only one case report in the literature (and not even searchable in Pubmed) of an actual burn from a TENS unit (14). In contrast, TENS therapy is actually used for pain relief on burn participants. Therefore, the risk of being burned from TENS therapy is extraordinarily low.

The effects of prolonged TENS usage have been studied in the literature before. The meta-analysis by Mark Johnson et al showed TENS units to be very safe with very few adverse effects seen even for more extended periods of use (10)

E. RISKS

The risks are minor and unanticipated. If there is any irritation to the participants skin due to the adhesive pads the participant will be treated and taken off the study.

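### Participants taken off the study for worsening before the 14-day visit can lack a Week 4 VAS and GUPI change score because of the outcome itself

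*Combined protocol and SAP*

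**What the plan says.** **Removal.** D. Data Analysis, Conduct of the study, covers participants whose symptoms are severe or keep worsening, and those with adverse reactions: "TENS therapy will be immediately discontinued, they will be removed from the study and considered to have failed treatment". They also receive medical treatment as needed. Such events come to light, among other routes, "by way of pain questionnaire, phone calls to participants, the 14-day clinic visits". E. Risks adds that for skin irritation from the pads "the participant will be treated and taken off the study".

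**Outcome and analysis.** The primary outcome is "percentage change in VAS and GUPI from before treatment to the end of 2 weeks of active TENS" (Outcome Variables and Schedule of Assessments). Under Statistical Methods, "Reduction will be parameterized as a relative change from baseline to after the two weeks of treatment", analysed by ANOVA with Tukey comparisons. VAS before and after treatment is compared by repeated measures ANOVA. No method for missing scores is given.

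**Analysis set.** The Intention-to-Treat section opens with the ITT principle, but a participant is then "included in the intention-to-treat analysis if the participant has documented at least 8 sessions of their designated TENS treatment".

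**Collection of scores.** Under Study Procedures, the Week 3 and Week 4 forms belong to the two weeks of active TENS use and are handed back around the 7-day and 14-day visits. The forms at 1, 2 and 3 months are for those who choose to go on with TENS. No VAS or GUPI is scheduled for someone who has been removed.

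**The concern.** Ordinary dropout may or may not relate to pain. Here one trigger for removal is worsening of the symptoms that the VAS and GUPI measure, and the pain questionnaire is one route by which it is detected. For those participants the protocol's own rule creates missing data that depend on the outcome. Those left for the change-score analysis then exclude some who did badly.

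If one frequency produced more worsening stops than the others, its observed mean change would look too good. The failure label does not repair this. It can be used as a responder value, but it is not a percentage change. For stops in the first treatment week it also meets the 8-session rule, and the plan does not say which prevails. If the session rule does, early failures drop out of the responder comparison as well.

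**Working it through.** **The plan's own figure.** Sample Size Considerations gives 81% power with 21 per group, for a difference of one within-group SD of the change in VAS at alpha 0.05. Take group means of -0.5, 0 and +0.5 SD:

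- Noncentrality = 21 × (0.25 + 0 + 0.25) = 10.5, with 2 and 60 degrees of freedom.
- Power = 81.5%. The stated figure reproduces, so the SD scale below is the plan's own.

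**Who lacks a Week 4 score.**

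- Worsening found at the 14-day visit: a Week 4 score can still be obtained, so there is no gap.
- Stop in the second treatment week: a Week 3 score will often exist, but the Week 4 value is missing and no rule says how to use Week 3 in its place.
- Stop before the Week 3 form: there may be no score under treatment at all.

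**Session count.** At one session a day, a stop on day 7 or earlier gives at most 7 sessions. Since 7 < 8, the participant is outside the set called ITT, although also counted as a treatment failure.

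**Size, as an illustration.** The documents give neither stop rates nor the outcomes of those who stop. Assume that in one arm *s* more participants stop than in the others, and that they would have ended *d* SD worse than those who stay. That arm's observed mean is then too favourable by (*s*/25) × *d*:

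- *s* = 2: 2/25 × 0.5 = 0.04 SD; 2/25 × 1.0 = 0.08 SD.
- *s* = 5: 5/25 × 0.5 = 0.10 SD; 5/25 × 1.0 = 0.20 SD.

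For the type I error, take three truly equal arms, within-arm SD 1, and one arm of *n* observed participants shifted by the bias *b*. The noncentrality is *n* × *b*² × 50/(*n* + 50), used in the noncentral F distribution:

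| Observed n | Shift (SD) | Noncentrality | Type I error |
|---|---|---|---|
| 23, 25, 25 | 0.04 | 0.025 | 5.2% |
| 23, 25, 25 | 0.08 | 0.101 | 5.7% |
| 20, 25, 25 | 0.10 | 0.143 | 6.0% |
| 20, 25, 25 | 0.20 | 0.571 | 9.3% |

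The five-stop rows use up one arm's whole 20% dropout allowance (0.20 × 25 = 5) on outcome-related stops and are an extreme case.

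**Upper bound.** A simulation deleted exactly the worst outcomes in one arm of 25 only. It gave a type I error of about 8.5% with two deleted and about 21% with five. Part of that excess is not bias between arms: deleting the five worst in every arm left no mean difference, yet still rejected about 13% of the time, because cutting off a tail shrinks the within-arm spread.

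**Rescue treatment.** If two of 25 receive rescue and improve by 0.5-1.0 SD, the arm mean rises by 2/25 × 0.5 to 2/25 × 1.0 = 0.04-0.08 SD. That is as large as the bias in the two-stop case, so a Week 4 score taken after rescue does not settle the matter alone.

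**The case against.** The strongest reply is that the effect is conditional and probably small. Equal stops with an equal link to outcome give no between-arm bias, and nothing in the documents says that stops differ by frequency. Sections A, D and F describe adverse effects of TENS as few or rare, which makes five extra stops in one arm an unlikely planning case. This stands as to size, although those statements concern adverse effects and not worsening pelvic pain.

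A second reply is that scores are weekly, so a second-week stop will often have a Week 3 score that the planned week-to-week analysis could use. This narrows the gap, but the primary Week 4 value is still missing.

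Third, F. Benefits foresees follow-up after treatment, so removal need not end clinical contact. But that follow-up is about whether TENS should resume, and no outcome collection is named.

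Stronger readings are tempting, but the text does not support them:

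- *The comparison of frequencies is biased.* This needs a difference between arms that no section reports or predicts.
- *Every removal depends on the outcome.* Pad irritation and other adverse reactions lose data but need not be related to pelvic pain.
- *Early failures are certainly lost from the responder analysis.* The failure label and the 8-session rule conflict, and the plan does not rank them.

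**Conclusion.** The point holds as a gap in data collection. Following the protocol as written can leave the primary Week 4 change score missing for participants removed for worsening before the 14-day visit, and the analysis section has no rule for them. For stops on days 1-7, the failure rule and the 8-session rule contradict each other.

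The consequence for the between-arm comparison is possible, not shown. With two extra stops in one arm it is 0.04-0.08 SD against a 1 SD target, and a type I error of about 5.2-5.7%. It reaches 0.10-0.20 SD and about 6-9% only in the extreme five-stop case. These figures rest on an assumed deficit of 0.5-1.0 SD, on an excess of stops in one arm only, and on a within-arm SD of 1. The case for change rests on the low cost of the remedy and on the fact that the missing scores cannot be obtained afterwards.

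**What to change.** In Conduct of the study and in E. Risks, separate stopping TENS from leaving the study. The clinical rules for stopping TENS stay as they are.

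1. **Collection.** Unless consent is withdrawn, obtain the Week 3 and Week 4 VAS and GUPI on their scheduled dates by Qualtrics or virtual visit. Where feasible, take a VAS and GUPI at the time of stopping, before any rescue treatment. Record the stop date, the reason and any new treatment on the Treatment Map.
2. **Analysis set.** Analyse all available scores by randomised arm whatever the number of sessions. Use the 8-session rule only for the per-protocol set.
3. **Responders.** Count worsening stops as non-responders whatever their session count. This settles the conflict between the two rules.
4. **Sensitivity analysis of change scores.** Limit it to participants who stopped for worsening or started rescue treatment for pelvic pain. Use the score at stopping, before rescue. Where none exists, assign a worse-than-baseline value over a stated range. Zero change would be too favourable for someone removed because of worsening. Do not overwrite the observed scores of participants who stopped for pad irritation and had no rescue for pelvic pain.

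The cost is a wording and consent amendment, one to three remote questionnaires for each person who stops, and one added analysis. The Qualtrics links, virtual visits and Treatment Map are already planned, and the sample size does not change.
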